3.2.2 Secondary

Secondary behavioral outcomes and process variables of interest are:

- **Smoking abstinence** assessed at 2 month follow-up (7 day point prevalent abstinence [PPA] with missing cases imputed). Additionally, we will assess abstinence at 2 and 6 months using a complete case (respondent only) analysis where missing data values are not imputed, to determine if imputation has a meaningful effect on the study results.
- We will assess whether groups differ in terms of the proportion of participants who either seek professional dental care following enrollment or have a future appointment scheduled at 6 months.
- Change in **oral health knowledge** from baseline to 2 and 6 month follow-up will be assessed using a scale adapted from Brennan et al⁴⁵ to address oral health behaviors (as opposed to tooth decay); include smoking, alcohol use, sugar free gum, and fruits and vegetables intake; and modify scripting for better phone delivery.
- Change in self-reported **self-efficacy** and **motivation** from baseline to 2 and 6 month follow-up. Self-efficacy and motivation will be assessed using a 5 point Likert-type scale.

3.2.2.1 Customer Satisfaction and Qualitative Feedback

Feedback will be collected at the end of the 6 month assessment. All participants will be asked to rate how helpful and how satisfied they were with each component of the

UC intervention (e.g., calls with a quit coach, Quit for Life stop smoking website, mailed stop smoking materials, nicotine replacement, etc.). Helpfulness and satisfaction will be rated on a 5-point Likert scale from “not at all” to “helpful”. Participants receiving the enhanced intervention will also rate each component of the Oral Health 4 Life program (e.g., oral health counseling, mailed materials, log-in secured website, oral health aids, referral information for low cost dental care, etc.). Finally, enhanced intervention participants will be asked a series of open-ended questions about which enhanced intervention components they used, what they liked best, and what they liked least. Responses will be transcribed verbatim for future content analysis.

3.2.2.2 Cost Analysis Measures and Outcomes

Because the goal of the current study is to assess the degree to which the Oral Health 4 Life program increases the likelihood of both quitting smoking and visiting a dentist and each of these outcomes may be of interest to different purchasers, we will provide a detailed assessment of the costs for each outcome. The analysis will examine the incremental cost of adding the Oral Health 4 Life program to the standard quitline program from the purchaser/payer perspective.

We will assess the estimated additional **cost per counseling call** for which the Oral Health 4 Life program is included and the **cost per successful cessation event**, based on six month outcomes. These calculate these costs we will estimate all resources required to develop and maintain the intervention materials (print and web-based), the increased personnel time to provide oral health counseling, and other outreach services related to Oral Health 4 Life (e.g., text messaging). All associated effort, labor costs, and material costs associated with delivering of the intervention will be tracked at GHRI and Alere.

We will also calculate the **cost per dental visit** attributable to the Oral Health 4 Life program and the **cost per both a successful cessation event and dental visit**, each assessed based on primary 6 month outcomes. The **cost per dental visit** will be assessed as the amount reimbursed by providers for routine preventive office visits. This is appropriate because our analysis takes the payer/provider perspective and while the amount reimbursed per visit is not the cost incurred by the practice it does capture the payer's financial responsibility. We will not include patient incurred costs, whether due to lost productive time or out of pocket expenses, because these costs are not the payer's responsibility. Because we will not have claims data containing details about specific reimbursable services provided at each visit attributable to the Oral Health 4 Life program, we will assign the mean dollar amount dental practices are reimbursed for

preventive visits based on relative resource intensity weights using the American Dental Association's Current Dental Terminology (CDT) coding scheme.

These data will then inform the creation of a 'willing to pay' decision support tool for future quitline sponsors that will allow purchasers (e.g., state departments of health) to calculate the cost per quit and cost per dental visit using data from the study.

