5.4 Treatment Assignment Procedures

5.4.1 Randomization Procedures

Eligible participants who provide consent will be block randomized using an automated algorithm built into the Alere systems software. Randomization will be stratified based on whether participants have dental insurance coverage [yes/no] and which tobacco quitline they are enrolled in [Louisiana, Nebraska or Oregon], to ensure balance across each treatment arm. Participants will then be randomly assigned to either the usual care quitline program or an enhanced quitline program (usual care tobacco quitline program + multi-modal oral health promotion intervention).

Randomization assignments will be monitored by the study biostatistician to confirm balanced assignment between groups. Unless anomalies are noted in the group assignments, such as due to a programming error, no changes will be made to the randomization code.

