Economic Analyses. In addition to addressing the main scientific aims above, we will calculate the incremental cost of adding the Oral Health 4 Life program, from the perspective of a future payer, and produce a decision support tool that will allow quitline sponsors to determine whether, based on their own willingness to pay for quitline services, adding the Oral Health 4 Life program makes economic sense. This deliverable reflects quitline purchasers' concerns about program cost. The decision support tool will be created on a standard Excel spreadsheet and distributed at no cost to any individual or group wishing to assess the financial viability of adding the Oral Health 4 Life program to their quitline calls. The decision tool will have three components. The first is a detailed model of the cost associated with the oral health program. To generate this model component we will use activity accounting methods,⁵¹ which uses micro-costing to assign unit costs to every physical and human resource required to deliver an intervention or program. To micro-cost the additional cost of oral health counseling we will identify each resource required to add this component including development and training time, supplies, the additional time spent per call, etc. The second component of the decision tool is the probability of success for each positive outcome (cessation, dental visit, both) associated with a quitline program incorporating Oral Health 4 Life. This information will be based on trial results and we will incorporate uncertainty by using confidence intervals derived from the analyses of our trial data as described above. The third component will be a user entered factor based on their willingness to pay so that a potential sponsor of Oral Health 4 Life can assess, based on alternative assumptions about cost, programmatic success and

willingness to pay, whether investing in the Oral Health 4 Life program makes financial sense to them. Each user will have the ability to vary each model parameter to determine the circumstances under which they would be willing to invest in purchasing the Oral Health 4 Life program. Thus, each purchaser can decide for themselves what outcomes could be expected based on the amount they are willing to pay. This tool will be shared with quitline purchasers to inform individual decisions about whether the program provides sufficient perceived value to warrant program costs.

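### The cost analysis does not say whose cost is counted: section 3.2.2.2 applies one mean reimbursement to all attributable dental visits whatever the dental cover, yet excludes out-of-pocket costs, and section 12.4 lists no reimbursement

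*Combined protocol and SAP*

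**What the plan says.** The perspective is worded three ways. Section 3.2.2.2 first examines the incremental cost "from the purchaser/payer perspective". Later in the same section, the dental-visit value is defended on the ground that "our analysis takes the payer/provider perspective". Section 12.4 (Economic Analyses) works "from the perspective of a future payer".

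On valuation, section 3.2.2.2 says the cost per dental visit "will be assessed as the amount reimbursed by providers for routine preventive office visits". Because there will be no claims data on the services given at each attributable visit, it adds that "we will assign the mean dollar amount dental practices are reimbursed for" preventive visits. It describes no split by insurance status. The same section states "We will not include patient incurred costs, whether due to lost productive time or out of pocket expenses", on the ground that these are not the payer's responsibility.

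On the user, the study data are to feed a decision tool that will "allow purchasers (e.g., state departments of health) to calculate the cost per quit and cost per dental visit". Section 3.1 identifies quitline sponsors as the potential purchasers.

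On insurance, section 5.4.1 stratifies randomisation by dental cover (yes or no), so both groups are enrolled and status is known at baseline.

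On the tool, section 12.4 describes three components: a micro-costing of the resources needed to deliver the programme (such as development and training, supplies and added call time), the probability of each outcome, and the user's willingness to pay. Dental reimbursement is not among the listed resources.

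**The concern.** A costing perspective decides which costs are in and which are out. Payer and provider sit on opposite sides of a reimbursement, and section 3.2.2.2 itself accepts that the reimbursed amount is not what the practice spends. Naming both leaves the reader unsure whose cost is reported.

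The valuation rule then conflicts with the exclusion rule. One mean reimbursement is attached to attributable visits, including those by participants without dental cover. Where such a participant pays, the plan enters as a payer cost an amount that its own rule keeps out.

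Two planned results are at stake: the cost per dental visit and the cost per quit plus dental visit. As written, two analysts could follow the plan and report different quantities under the same label.

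**Working it through.** The documents give no fee, reimbursement rate or share of participants without dental cover, so there is no stated cost figure to reproduce. The check compares the sections and then shows the size algebraically.

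**Step 1. Is the payer identified?** Section 3.2.2.2 names purchaser/payer, then payer/provider; section 12.4 names a future payer. The wording of the visit cost also reverses direction: in one sentence providers do the reimbursing, and in a later one dental practices receive the reimbursement. No sentence says who reimburses.

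**Step 2. Does the valuation obey the exclusion?** Let R be the mean reimbursement assigned per attributable visit and u the share of those visits not borne by the payer.

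- Assigned per visit: R
- Actually payer-borne per visit, on average: (1 - u)R
- Excess per visit: R - (1 - u)R = uR
- Overstatement of the dental component: R / [(1 - u)R] = 1/(1 - u)

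With assumed values of u:

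| u (assumed) | payer-borne | excess | factor |
|---|---|---|---|
| 0% | R | 0 | 1.00 |
| 25% | 0.75R | 0.25R | 1.33 |
| 50% | 0.50R | 0.50R | 2.00 |
| 75% | 0.25R | 0.75R | 4.00 |

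The two rules agree only at u = 0. The factor applies to the reimbursement component, not to programme cost.

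**Step 3. Does reimbursement enter the cost?** Take the dental rates in section 12.2 (5% usual care, 15% enhanced) and about 356 per arm (Protocol Summary).

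- Additional participants with a visit: 356 × (0.15 - 0.05) = 35.6
- Participants treated per additional visit: 1 / (0.15 - 0.05) = 10

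With C the programme cost per participant, the label cost per dental visit has three readings:

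- R, if it is the reimbursed amount alone (the literal wording of section 3.2.2.2)
- 10C, if only delivery resources count (the cost model in section 12.4)
- 10C + R, if reimbursement is added to programme cost

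The first does not depend on the trial's effect at all; the other two do. The plan does not say which is meant.

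**Step 4. How many visits would an insured-only figure rest on?** At the planned effect, 35.6 × (1 - u), taking u here as the share of those visits made by participants without cover: 26.7 at u = 25% and 17.8 at u = 50%. The dental outcome is yes/no per participant, so these are counts of participants with a visit.

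**The case against.** The best defence is that the mean reimbursement is an openly stated approximation. The plan explains that it will have no claims data, and a single unit cost is a common answer to that. Section 3.2.2.2 also expects the outcomes to interest different purchasers, so a mixed perspective may be an attempt to serve more than one. State health departments are given only as an example of a purchaser, and section 2.2 reports more people served under all of the vendor's contracts (nearly 352,000 in 2012) than under state contracts (more than 279,000). All of this stands. It argues for separate labelled results, but it does not remove the conflict with the out-of-pocket exclusion.

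Three stronger readings are tempting and are not supported.

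- A reader might infer that quitline sponsors never reimburse dental visits, so that the whole component is foreign to them. The programme as described offers referral information and supplies rather than paid visits, which makes the inference reasonable, but no section says it.
- A reader might infer that visits by participants without cover are entirely out of pocket. The programme refers people to low-cost care, and the documents do not say who funds it. This is why u is defined as the share not borne by the payer, and not as the uninsured share.
- A reader might infer that the decision tool would mislead sponsors. Section 12.4 lists only delivery resources on the cost side and lets each user vary every parameter, so that goes too far.

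It is also fair to object that baseline cover is only a proxy for who paid a later visit. That limits the fix and must be stated with it.

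**Conclusion.** The point holds in limited form. The perspective is inconsistent within section 3.2.2.2 and between it and section 12.4. The valuation rule, followed as written, counts as payer cost any attributable visit that the payer does not bear, contrary to the plan's own exclusion. The two sections also differ on whether reimbursement is part of the cost.

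The size cannot be fixed from the documents. The dental component is overstated by 1/(1 - u), which is 1.33 to 2 for assumed u of 25% to 50%, and not at all if u is zero. The effect on a combined figure such as 10C + R depends on C and R, neither of which is given.

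This is a minor point. It touches the dental-visit costing in a secondary economic output. The randomised comparison, both primary outcomes, the cost per call and the cost per quit are unaffected.

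**What to change.** 1. Name the payer, and use the same wording in both parts of section 3.2.2.2 and in section 12.4.
2. For the quitline purchaser, report programme cost per additional dental visit, and per quit plus visit, without reimbursement.
3. As a separate result labelled for a dental payer, add the mean reimbursement only for attributable visits by participants with dental cover at baseline, using the stratification variable. State that baseline cover is a proxy for who paid.
4. Show the assignment of reimbursement to all attributable visits as a sensitivity analysis.
5. Correct the phrase that has providers doing the reimbursing, and state in the description of the decision tool which of these costs it uses.

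The cost is a wording change and a subset calculation on a variable already held. The drawback is that two cost figures are reported instead of one, with the insured-only figure resting on fewer visits and so being less precise.

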4 STUDY DESIGN

We will conduct a randomized, two arm trial including a small vanguard wave (n up to ~30) followed by a larger intent to treat sample wave (n ~ 712). The design and methods used in each sample wave will be the same, except the vanguard will launch approximately 2 months prior to the main sample wave in order to pilot all methods and procedures and allow time to make adjustments, as necessary. Participants in the vanguard wave will not be included in the final analytic sample.

Participants will be smokers who call to enroll in services in one of the participating quitlines [Louisiana, Oregon, and Nebraska], meet eligibility criteria (see sections 5.1 and 5.2), and volunteer to participate in this study. Each person will be followed for 6 months and will complete phone surveys at baseline, 2 months post-enrollment, and 6 months post-enrollment.

While not a formal pragmatic trial, the study has been designed to be delivered under the conditions of real-world care provided by the tobacco quitlines. As a result, study assessments, consent processes, and other activities which are not part of the standard of care have been purposefully designed to be brief in order to minimize the impact on the standard flow of care, while still allowing us to assess the most important primary and secondary outcomes of interest.

Additionally, due to the nature of the trial, neither participants nor counselors (quit coaches) in the enhanced intervention (experimental arm) will be blinded to participants' treatment assignment. Quit coaches delivering usual care will be aware that participants' are enrolled in a non-standard contract (e.g., a research study), but they will not be trained in or exposed to the enhanced intervention to prevent contamination. Group Health research staff who conduct follow-up assessments will be blinded to treatment assignment.

5 STUDY ENROLLMENT AND WITHDRAWAL

5.1 Subject Inclusion Criteria

In order to be eligible to participate in this study, a participant must meet all of the following criteria (see also Eligibility Screen in Appendix D):

- Male or female, aged 18 or older
- Eligible for multi-call services through a participating tobacco quitline [in Louisiana, Nebraska, or Oregon] managed by Alere Wellbeing
- Can read and speak in English
- Able to comfortably read small print (i.e., no significant visual impairments that limit ability to read the intervention materials)
- Current daily smoker and smokes at least 5 cigarettes a day
- Interested in quitting smoking in next 30 days
- Have some or all natural teeth
- Have not visited a dentist for a checkup or teeth cleaning in the past 6 months and do not have an appointment scheduled in the next 6 months
- Has a cell phone capable of receiving text messages and provides cell phone number
- Has internet access for personal use
- Willing to talk about ways to improve their oral health
- Provides verbal consent to participate

5.2 Subject Exclusion Criteria

Individuals will be excluded if they:

- Self-report a diagnosis of bipolar disorder, mania, schizophrenia, dementia (e.g., has significant cognitive impairment)
- Plans to move in the next 6 months
- Are currently enrolled in an in-patient substance abuse treatment facility or are incarcerated

- Has a household member already enrolled in the study, based on self-report and/or mailing address on file

5.3 Strategies for Recruitment and Retention

Recruitment: Following completion of the normal tobacco quitline registration process, persons calling each of the eligible quitlines and who have not been deemed ineligible based on screening criteria which are collected as part of the normal intake will be informed of the study and invited to complete the eligibility screening process. If eligible and interested, potential participants will then be transferred to staff in the Research Implementation Unit (RIU). RIU staff will collect and document verbal consent. Responses will be recorded. Participants who provide consent will complete a baseline assessment and then be randomized to treatment using an automated algorithm, prior to the treatment initiation.

If participants do not complete the study enrollment call due to dropping off/hanging up the RIU coach will make five attempts on five separate days to be attempting to get them back to complete enrollment. Call attempts will begin the same day or the following day that the call is lost. One voicemail will be left for participants that consented to receiving voicemails during Registration. Staff will stop trying to enroll the participant after five call attempts go unanswered.

Retention: We will use standard procedures to ensure study retention, including offering an incentive for completion of each survey (\$30), sending reminder letters one week prior to each scheduled assessment and marked for return service requested, and using phone and internet records to track participants who move and do not have a change of address on file with the Post Office or Alere Wellbeing. Difficult to reach subjects will be texted an offer of an extra \$15 incentive if they call in to complete the survey by phone.

Phone counseling calls will be proactively scheduled and initiated by Alere quit coaches on the standard call schedule (see section 7.3). Consistent with standard practice as dictated by each quitline contract, at least 3 attempts will be made to complete each of the 5 counseling calls with all participants. Text messages are offered to all study participants. The text messages will be proactively delivered on a pre-determined schedule with automated delivery (see section 7.3).

Participants who request to drop out of the intervention will be asked if they are willing to remain in the study and be contacted for follow-up assessment. If not, they will be dropped from further contact.

5.4 Treatment Assignment Procedures

5.4.1 Randomization Procedures

Eligible participants who provide consent will be block randomized using an automated algorithm built into the Alere systems software. Randomization will be stratified based on whether participants have dental insurance coverage [yes/no] and which tobacco quitline they are enrolled in [Louisiana, Nebraska or Oregon], to ensure balance across each treatment arm. Participants will then be randomly assigned to either the usual care quitline program or an enhanced quitline program (usual care tobacco quitline program + multi-modal oral health promotion intervention).

Randomization assignments will be monitored by the study biostatistician to confirm balanced assignment between groups. Unless anomalies are noted in the group assignments, such as due to a programming error, no changes will be made to the randomization code.

5.4.2 Masking Procedures

Intervention: Due to the nature of the trial, neither participants nor counselors (quit coaches) in the enhanced intervention (experimental arm) will be blinded to participants' treatment assignment. Quit coaches delivering usual care will be aware that participants' are enrolled in a non-standard contract (e.g., a research study), but they will not be trained in or exposed to the enhanced intervention to prevent contamination.

Assessment: GHRI staff conducting follow-up assessments will be blinded to treatment assignment.

5.5 Subject Withdrawal

Subjects may withdraw voluntarily from the study or the investigator may terminate a subject's participation.

